### **5.6.3 Study Periods**

This is a randomized, placebo-controlled, single-dose, parallel arm study. Healthy subjects will be randomized to three dose groups (low, intermediate, and high) of each drug (Avonex or Plegridy) or placebo. Subjects randomized to the Avonex Treatment Groups (A-C) will be discharged on Day 7, while subjects randomized to the Plegridy or placebo Treatment Groups (D-G) will be discharged on Day 14.

#### **5.6.3.1 Check-in**

The following procedures and assessments will be performed at Check-in (Day -1):

- Perform/review results from SARS-CoV-2 molecular diagnostic test
- Review inclusion/exclusion criteria to confirm subject eligibility
- Review medical history
- Perform alcohol and drug screening (amphetamines, barbiturates, benzodiazepines, cannabinoids, cocaine, alcohol, opiates, phencyclidine, propoxyphene, and methadone)
- Perform a serum pregnancy test (female subjects only)
- Admit subject to the study clinic
- Randomization (after completion of check-in procedures on Day -1 or just before dosing on Day 1)
- Record concomitant medications
- Monitor for AEs
- Perform clinical laboratory tests (hematology, serum chemistry, and urinalysis)
- Measure vital signs (blood pressure, heart rate, respiratory rate, and oral body temperature)
- Perform a safety 12-lead ECG
- Perform a complete physical examination
- Collect whole blood for non-fasting lipid panel
- Collect whole blood (5 mL) and process for plasma for proteomic and small-RNA transcriptomic analyses
- Collect urine (3-5 mL) for omic analysis (e.g., transcriptomics and/or metabolomics)

### **5.6.3.2 Treatment**

The following procedures and assessments will be performed during the treatment period according to the Schedules of Events (Table 9-1):

- Record concomitant medications
- Monitor for AEs
- Perform clinical laboratory tests
- Administer study drug according to the randomization schedule following all other pre-dose examinations and specimen collection
- Perform a complete or targeted physical examination
- Measure vital signs (blood pressure, heart rate, respiratory rate, and oral body temperature)
- Perform safety 12-lead ECG. If scheduled for the same time, the safety 12-lead ECG will always be performed before vital sign measurement and blood sample collection
- Perform alcohol and drug screening (amphetamines, barbiturates, benzodiazepines, cannabinoids, cocaine, alcohol, opiates, phencyclidine, propoxyphene, and methadone)
- Perform a serum pregnancy test (female subjects only)
- Collect PK/neopterin blood samples (5 mL). There are no washout periods for this study.
- Collect whole blood for MxA analysis (1 mL)
- Collect buffy coat for genomic analyses
- Collect whole blood for non-fasting lipid panel
- Collect whole blood (5 mL) for plasma proteomic and small RNA transcriptomic analyses
- Collect urine (3-5 mL) for omic analysis (e.g., transcriptomics and/or metabolomics)

### **5.6.4 Discharge (or Early Termination)**

The following procedures and assessments will be performed before the subject is discharged from the study (Day 7 or Day 14) or at early termination:

- Perform a serum pregnancy test (female subjects only)
- Record concomitant medications
- Monitor for AEs

- Perform clinical laboratory tests (hematology, serum chemistry, and urinalysis)
- Measure vital signs (blood pressure, heart rate, respiratory rate, and oral body temperature)
- Perform a safety 12-lead ECG
- Perform a complete physical examination
- Measure height, weight, and calculate body mass index
- Perform serology screening
- Perform alcohol and drug screening (amphetamines, barbiturates, benzodiazepines, cannabinoids, cocaine, alcohol, opiates, phencyclidine, propoxyphene, and methadone)
- Collect a single PK/neopterin blood sample (5 mL)
- Collect whole blood for MxA analysis (1 mL)
- Collect whole blood for non-fasting lipid panel
- Collect whole blood (5 mL) for plasma proteomic and small RNA transcriptomic analyses
- Collect urine (3-5 mL) for omic analysis (e.g., transcriptomics and/or metabolomics)
- Remove IV catheter (if applicable)
- Discharge subject from the study clinic after completion of all study procedures

## **5.7. Study Procedures**

### **5.7.1 Pharmacokinetic Assessments**

#### **5.7.1.1 Pharmacokinetic Sample Collection**

Pharmacokinetic blood samples (5 mL) will be collected at the following time points:

- Day 1: 0 (predose), 1, 3, 6, 8, 16, 24 h
- Day 2: 32, 40, 48 h
- Day 3, 4, 5, 6, 7, 8\*, 9\*, 10\*, 14\*

\*After Day 7 for peg-interferon beta-1a (Plegridy) only

Blood samples will be collected by direct venipuncture or by inserting an IV catheter into the subject's forearm region. Each blood sample will be labeled with subject number, study number, study day, time point, event, and a barcode that matches that belonging to the subject.

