## 5. Investigational Plan

### 5.1. Study Design

This is a randomized, placebo-controlled, single-dose, parallel arm study. Healthy subjects will be randomized to three dose groups (low, intermediate, and high) of each drug (interferon beta-1a [Avonex] and peginterferon beta-1a [Plegridy]) or placebo (see Table 5-1).

Subjects will report to the study site for screening assessments from days -21 to -2 and then will return to the site on day -1 for baseline assessments. Prior to and following study drug or placebo administration on day 1, they will undergo assessments as described in Table 9-1. Subjects randomized to Treatment Groups A-C will stay in house for the duration of the study and will be discharged on Day 7. Subjects randomized to Treatment Groups D-G will stay in house for the duration of the study and will be discharged on Day 14. Each treatment group should include equal representation of male and female subjects.

Depending on the treatment arm, subjects will have up to a maximum of 20 PK and PD blood draws and additional study procedures as outlined in the schedule of events.

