## **5.7.2 Pharmacodynamic Assessments**

### **5.7.2.1 Pharmacodynamic Sample Collection**

#### **5.7.2.1.1 Primary and Secondary PD Biomarker**

The PK blood samples collected (5 mL) will be used for the primary PD biomarker (neopterin) analysis and will be collected according to the schedule in Section 5.7.1.1. Blood samples (1 mL) for the secondary PD biomarker (MxA) analysis will be collected at the same time points as the PK/neopterin samples.

Blood samples will be collected by direct venipuncture or by inserting an IV catheter into the subject's forearm region. Each blood sample will be labeled with subject number,

study number, study day, time point, event, and a barcode that matches that belonging to the subject.

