## 7.5. PK/PD Analyses

The dose- and exposure-response relationship between baseline-adjusted AUEC for neopterin and  $\Delta\text{Neopterin}_{\text{dec, max}}$  and IFN  $\beta$ -1a and pegIFN  $\beta$ -1a will be explored graphically (separate assessments for both response measures). Based on these observations, model-based analyses using statistical software will be conducted separately for each drug with respect to each of the above-mentioned PD measures.

The model-based analysis will explore both dose and exposure (i.e.,  $AUC_{0-\text{inf}}$ , referred to as AUC below) as the dependent variable. Data for all dose levels for a drug, as well as placebo, will be combined for the analysis. Model selection will be based on the initial graphical assessment and will be selected from one of the following structures – linear,  $E_{\text{max}}$ , and sigmoidal. Multiple models may be evaluated based on the initial graphical analysis, in which case model selection will be based on a combination of goodness of fit plots, parameter uncertainty (i.e., parameter confidence intervals including zero), and Akaike’s information criterion (AIC). General representations for each of the model structures and parameterizations is shown below:

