### **Pharmacodynamic Sample Collection**

Blood samples for primary pharmacodynamic biomarker (neopterin, 5 mL) and secondary pharmacodynamic biomarker (MxA, 1 mL) assessments will be collected at the following time points:

- Screening (Day -21 to -2)
- Day 1: 0 (pre-dose), 1, 3, 6, 8, 16 h
- Day 2: 24, 32, 40 h
- Day 3, 4, 5, 6, 7
- Day 8, 9, 10, and 14 (Arms D, E, F, and G, only)

Blood samples will be collected by direct venipuncture or by inserting an IV catheter into the subject's forearm region. Each blood sample will be labeled with subject number, study number, study day, time point, event, and a barcode that matches that belonging to the subject.

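### Protocol and SAP disagree on whether placebo is sampled after Day 7, and the SAP sets no common AUEC window when it pools placebo with each drug

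*Protocol*

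**What the plan says.** **Sampling after Day 7.** Protocol 5.7.1.1 marks Days 8, 9, 10 and 14 with the note "After Day 7 for peg-interferon beta-1a (Plegridy) only". Section 5.7.2.1.1 extends this beyond PK: neopterin samples "will be collected according to the schedule in Section 5.7.1.1" and MxA samples "will be collected at the same time points as the PK/neopterin samples". Section 5.7.2.1.2 repeats the restriction for the exploratory markers. SAP Attachment A instead lists "Day 8, 9, 10, and 14 (Arms D, E, F, and G, only" for neopterin and MxA, and names the same arms for PK and the exploratory markers. Arm G is placebo. The SAP change log does not mention a change here.

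**Placebo follow-up.** The protocol keeps placebo on study as long as Plegridy. Section 5.1 says Groups D-G "will stay in house for the duration of the study and will be discharged on Day 14", and 5.6.3 agrees ("while subjects randomized to the Plegridy or placebo Treatment Groups (D-G) will be discharged on Day 14"). Section 5.6.4 lists procedures to be done "before the subject is discharged from the study (Day 7 or Day 14) or at early termination". The list includes one PK/neopterin sample and one MxA sample, with no exception for placebo.

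**Use in the model.** SAP 7.5 says: "Data for all dose levels for a drug, as well as placebo, will be combined for the analysis". Protocol 5.9.6.1 pools in the same way. SAP 4.1 runs AUEC from time zero to the last on-study time point, and SAP 7.5 models the baseline-adjusted version. Neither document sets a common end time for arms that are pooled.

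**The concern.** Placebo anchors E0 in the dose- and exposure-response models of both drugs. A site working from the protocol's lists would leave most of the second week of placebo unsampled, and undrawn samples cannot be recovered at analysis. Drift or baseline noise in that week of the Plegridy profile would then have little or no placebo reference.

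The second issue is the window. Each subject's AUEC ends at that subject's last sample, so pooled arms can cover different lengths of time. The SAP 7.5 models contain an E0, a dose or exposure term and a residual error, with no random effects or covariates. Nothing in them absorbs a difference in window length. This arises on the SAP's own schedule too, because Avonex stops at Day 7 and placebo runs to Day 14.

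**Working it through.** The documents give no figure for this point, so there is none to reproduce.

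**1. Placebo time points after Day 7** (12 subjects; neopterin and MxA each)

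- SAP Attachment A (Days 8, 9, 10, 14): 12 × 4 = 48.
- Protocol 5.7.1.1 note alone: 0.
- Protocol with the 5.6.4 discharge samples on Day 14: 12 × 1 = 12.
- Certain gap between the lists (Days 8, 9, 10): 12 × 3 = 36. The other 12, on Day 14, depend on which protocol section governs.

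**2. AUEC windows** (assumption: nominal time of Day d is (d − 1) × 24 h)

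- Day 7: 6 × 24 = 144 h. Day 14: 13 × 24 = 312 h.
- Day 7 to Day 14: 312 − 144 = 168 h, or 168/312 = 54% of the long window.

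| Schedule followed | Avonex | Plegridy | Placebo | Model with unequal windows |
|---|---|---|---|---|
| SAP Attachment A | 144 h | 312 h | 312 h | Avonex |
| Protocol, 5.7.1.1 note governs Day 14 | 144 h | 312 h | 144 h | Plegridy |
| Protocol, 5.6.4 governs Day 14 | 144 h | 312 h | 312 h, nothing between Days 7 and 14 | Avonex |

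**3. Noise in baseline-adjusted AUEC**

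Assume each sample carries independent noise with the same SD, s. Use the trapezoidal rule on the SAP times: 0, 1, 3, 6, 8, 16, 24, 32, 40 h, Days 3 to 7 (48 to 144 h), then 168, 192, 216 and 312 h where drawn. With trapezoid weights w_i and window T, subtracting the pre-dose value across the window gives

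Var = s² × [(T − w_0)² + Σ w_i² over post-dose samples], with w_0 = 0.5 h.

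- To Day 7: 143.5² + 2,423.75 = 23,016, so SD = 152s.
- To Day 14, all samples: 311.5² + 9,911.75 = 106,944, so SD = 327s.
- To Day 14, with Days 8, 9 and 10 missing: 311.5² + 18,551.75 = 115,584, so SD = 340s.

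Ratio of long to short window: 327/152, which is 2.16 before rounding. Omitting Days 8, 9 and 10 while keeping Day 14 raises the noise SD by only about 4% (340/327).

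**4. Drift**

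A constant shift of δ from the pre-dose value, unrelated to drug, contributes 144δ to the short window and 312δ to the long one. The difference of 168δ falls between pooled arms, and the model can only assign it to E0 or to the drug term.

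**The case against.** The strongest reply is that the protocol does obtain a placebo value at the end of the second week. Section 5.6.4 applies to everyone discharged on Day 14, so each completing placebo subject gives neopterin and MxA then. This stands. A reader might infer that the Plegridy model has no placebo data at all for Days 8 to 14, but the documents do not support that. Only Days 8, 9 and 10 are certainly missing from the protocol's placebo lists. What the reply leaves is a contradiction within the protocol on Day 14 and, if 5.6.4 governs, a single 168 h trapezoid in place of four sampled points.

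A reader might also infer that AUEC is inflated by 312/144 = 2.17 in the longer-sampled arms. That ratio belongs to raw AUEC, which is not the model input. With neither drug effect nor drift, baseline-adjusted AUEC has expectation zero for any window length. The window then affects noise and drift, as computed above.

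Three further replies have partial force.

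- The protocol truncates AUEC after return to baseline, with separate intervals per dose, which would lessen the effect. The SAP endpoint, however, runs to the last on-study time point.
- Pairing the protocol's sampling list with the SAP's AUEC mixes two plans. That is fair for the Plegridy mismatch, but the Avonex mismatch arises within the SAP alone.
- Table 9-1 is the protocol's reference for time points and was not in the text supplied for review. The 5.7.1.1 note may be shorthand separating Plegridy from Avonex, with placebo meant to follow Plegridy. The table could show what was intended, but the conflicting lists would still need correction.

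**Conclusion.** The point holds in two parts.

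1. The documents conflict on placebo sampling after Day 7: protocol against SAP for Days 8, 9 and 10 (36 of 48 planned placebo time points), and the protocol against itself for Day 14.
2. SAP 7.5 pools arms with unequal AUEC windows, 312 h against 144 h, in at least one drug's model however the sampling conflict is settled. Under the SAP schedule, or if 5.6.4 governs, it is the Avonex model. If the 5.7.1.1 note governs Day 14, it is the Plegridy model.

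In the affected model the longer-window arms carry about 2.16 times the noise SD, and drift accrues over 168 h more. The 2.16 assumes equal independent noise per sample, nominal times and trapezoidal AUEC. It describes the noise component only, not variation between subjects in response. The size of any drift is not given in the documents. What the site would actually do depends on Table 9-1, which should be checked.

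A reader might go on to conclude that Plegridy-with-placebo models must stop at Day 7. That does not follow unless placebo truly has no sample after Day 7. Otherwise it would discard 54% of the Plegridy window needlessly.

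**What to change.** - **Sampling lists.** Align protocol 5.7.1.1, 5.7.2.1.2, 5.6.4 and Table 9-1 with SAP Attachment A, so that all name the same arms for Days 8, 9, 10 and 14. The SAP already plans placebo sampling on these days, and placebo subjects are on study to Day 14.
- **AUEC window.** State in SAP 7.5 that, in each drug's model, placebo AUEC is computed to the same nominal end time as that drug's arms: Day 7 for Avonex, Day 14 for Plegridy. Only if placebo has no sample after Day 7 should the Plegridy-with-placebo model stop at Day 7, with the later Plegridy data reported descriptively.

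The cost is wording in both documents. Relative to the protocol's lists, sampling placebo adds three draws per subject in 12 subjects if 5.6.4 already supplies Day 14, and four if it does not. Relative to the SAP it adds none. The window rule needs no new data.

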### **5.7.1.2 Pharmacokinetic Specimen Handling**

The PK blood samples (5 mL each) will be collected into vacutainer tubes and allowed to clot at room temperature for at least 30 min (not exceeding 60 mins). Within 60 minutes of collection, the samples will be centrifuged for 15 minutes, at 2000 g, at 4°C, by a study team member.

The serum will be separated using a disposable plastic pipette and approximately equal volume of serum will be aliquoted into four aliquots Aliquot A (primary) and aliquots B, C & D (back-up). The serum samples will be appropriately labeled and stored frozen at –80°C or below until shipment. Temperature monitoring logs should be maintained and accessible for review by the study monitor.

The Aliquot A samples (primary) will be shipped first, on dry ice, to the bioanalytical laboratory at FDA for processing when requested by the sponsor. The backup aliquots sample will be held for a further shipment which will be communicated by the sponsor. None of the PK blood samples will be stored for other analyses not specified in this protocol.

### **5.7.1.3 Pharmacokinetic Parameters**

The following PK parameters will be determined for each subject:

- Maximum concentration (observed peak drug concentration) (Cmax)
- Time at which Cmax occurs (Tmax)
- AUC from time 0 to the sampling time corresponding to the last quantifiable concentration (Clast) (AUC0-t)
- Elimination rate constant (Kel)
- Terminal half-life (t1/2)
- AUC from time 0 extrapolated to infinity (AUC0-inf)

## **5.7.2 Pharmacodynamic Assessments**

### **5.7.2.1 Pharmacodynamic Sample Collection**

#### **5.7.2.1.1 Primary and Secondary PD Biomarker**

The PK blood samples collected (5 mL) will be used for the primary PD biomarker (neopterin) analysis and will be collected according to the schedule in Section 5.7.1.1. Blood samples (1 mL) for the secondary PD biomarker (MxA) analysis will be collected at the same time points as the PK/neopterin samples.

Blood samples will be collected by direct venipuncture or by inserting an IV catheter into the subject's forearm region. Each blood sample will be labeled with subject number,

study number, study day, time point, event, and a barcode that matches that belonging to the subject.

### **5.7.2.1.2 Exploratory PD Biomarkers**

Exploratory PD biomarkers will be evaluated using plasma proteomics and small RNA transcriptomics. Whole blood samples (5 mL) will be collected and processed for plasma at the following time points:

- Day 1: 0 (predose), 1, 3, 6, 8, 16, 24 h
- Day 2: 32, 40, 48 h
- Day 3, 4, 5, 6, 7, 8\*, 9\*, 10\*, 14\*

\*After Day 7 for peg-interferon beta-1a (Plegridy) only

Blood samples will be collected by direct venipuncture or by inserting an IV catheter into the subject's forearm region. Each blood sample will be labeled with subject number, study number, study day, time point, event, and a barcode that matches that belonging to the subject. All blood samples will be processed for preparation of plasma.

### **5.7.2.2 Pharmacodynamic Specimen Handling**

#### **5.7.2.2.1 Primary and Secondary PD Biomarker**

The PD blood samples for the primary biomarker (neopterin) will be the same samples taken for the PK analysis. These samples will be collected and handled as described in Section 5.7.1.2.

The PD blood samples (1 mL) for MxA analysis will be collected and diluted with 9 mL of MxA assay lysis buffer (which will be provided by FDA). This diluted blood will be aliquoted to 5 tubes of equal volume and be frozen at -80°C until shipment.

#### **5.7.2.2.2 Exploratory PD Biomarkers**

Whole-blood samples will be collected at each time-point specified (Table 9-1).

Approximately 5 mL per patient will be collected and processed to provide plasma for proteomics and small-RNA transcriptomics.

Whole blood should be collected in BD Vacutainer® Venous Blood Collection Tubes containing EDTA (or any other primary blood collection tube containing EDTA as anticoagulant) and stored at room temperature (15–25°C) or 4°C before processing within 1 hour. Heparin-containing blood collection tubes should not be used as this anticoagulant can interfere with downstream analyses.

Plasma samples should be processed, aliquoted (approximately 500  $\mu$ L volumes), and placed into the -80C freezer within 2 hours of collection.

### **5.7.2.3 Pharmacodynamic Parameters**

#### **5.7.2.3.1 Primary and Secondary PD Biomarker**

The following PD parameters will be determined for each subject:

- Area under the effect curve (AUEC) change from baseline truncated after return to baseline
- Percentage area under the effect curve (pAUEC) change from baseline truncated after return to baseline
- Maximum change from baseline at single time-point ( $E_{max}$ )

#### **5.7.2.3.2 Exploratory PD Biomarkers**

The following PD parameters of the exploratory biomarkers will be assessed for all subjects:

Plasma proteome and small RNA transcriptome: Circulating proteins and small RNAs across ten or more specific time-points (to allow modeling of AUEC) and multiple drug doses will be evaluated using a systematic approach to discovery and replication of PD biomarkers and/or hypothesis-generation. Differential expression analysis (as well as candidate pathway analyses) of proteomic and small RNA data will be performed, respectively, at specified time points in the higher dose groups (discovery phase). Any promising PD biomarkers or patterns identified in this phase will then be independently and technically evaluated for differential expression in the remaining intermediate and low dose groups (replication and technical validation phase).

### **5.7.3 Additional Assessments**

#### **5.7.3.1 Sample Collection**

Samples for genomic or other omic biomarker assessment will be collected at the following time points:

- Buffy coat: Day 1 (Pre-dose)
- Urine Sample Collection: Screening, Day -1 (check-in), Day 1 (pre-dose and 24 hours), and Day 3, 5, 7, and 14

These samples will be used for analyses that will be considered hypothesis-generating and exploratory. All sample analysis will be performed by DARS staff.

### **5.7.3.2 Specimen Handling**

A buffy coat from each study participant will be used for exploratory genomic analyses. On the specified collection day/time (Day 1, pre-dose), 5 mL of whole blood sample will be processed for plasma and the upper plasma phase will be transferred to a new sterile Falcon tube without disturbing the intermediate buffy coat layer. The buffy coat layer will then be transferred to a sterile 2 mL Eppendorf (safe-lock) tube (on wet ice). Buffy coat samples should be immediately frozen in a dry ice/ethanol bath (for ~ 40 seconds) and then transferred to a -80°C freezer. Only sterile (nuclease-free) plastic pipettes, pipette tips and tubes should be used. All barcoded buffy coat Eppendorf tubes should be frozen and stored at -80°C as described above until appropriately transported to the FDA for long-term storage. Sample analysis will be performed by DARS research staff.

At specified times for urine sample collection, 3-5 mL of urine will be processed according to the SOP, separated into 6 approximately equal aliquots, immediately frozen in a dry ice/ethanol bath (for ~40 second or until frozen), and then immediately transferred to -80°C for long-term storage. Sample analysis will be performed by DARS staff.

